7.2 Classification of an Adverse Event

Severity of Event 7.2.1

The severity of each AE will be graded on a 3-point scale and reported in detail as indicated on the eCRF:

- Mild: awareness of sign or symptom but easily tolerated, causing minimal discomfort, and not interfering with normal everyday activities
- Moderate: sufficiently discomforting to interfere with normal everyday activities

Study: ACP-2566-009
Clinical Study Protocol Amendment 2

• Severe: incapacitating and/or preventing normal everyday activities

7.2.2 Relationship to Study Drug

The causality of each AE should be assessed and classified by the Investigator as "related" or "not related." An event is considered related if there is a reasonable possibility that the event may have been caused by the product under investigation (i.e., there are facts, evidence, or arguments to suggest possible causation).

Consider the following when assessing causality:

- Temporal associations between the agent and the event
- Response to cessation (de-challenge) or re-challenge
- Compatibility with known class effect
- Known effects of concomitant medications
- Pre-existing risk factors
- A plausible mechanism
- Concurrent illnesses

7.2.3 Duration

The start and stop dates for AEs will be recorded using the following criteria:

- **Start:** Date of the first episode of the AE or date of significant sustained worsening in severity
- Stop: Date when AE either ceased permanently or worsened in severity

For AEs of diarrhea, the start date and stop date of a decrease in severity will also be recorded.

7.2.4 Frequency

The frequency of the AE should be indicated according to the following definitions:

- **Single:** Experienced once, without recurrence
- **Recurrent:** More than one discrete episode with the same severity

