3 STUDY DESCRIPTION

3.1 Overview of Study Design

This is a multicenter, open-label study of trofinetide for the treatment of girls 2 to 5 years of age with RTT. Participating girls 2 to 4 years of age must weigh \geq 9 kg and \leq 20 kg. Girls 5 years of age who weigh \geq 9 kg and \leq 12 kg can also be enrolled.

Study: ACP-2566-009 Clinical Study Protocol Amendment 2

Approximately 10 to 15 subjects are expected to be enrolled, at least 1 subject who weighs ≥9 to <11 kg, and at least 4 subjects who are less than 4 years of age at Screening, including at least one subject who is 2 years of age. Approximately 10 sites will participate in this study.

The duration of the study will be 26 months and will have three main periods (Figure S-1):

- Screening period: up to 4 weeks
- Treatment period

o Period A: 12 weeks

o Period B: up to approximately 21 months

• Safety follow-up period: 30 days

The schedule of events and assessments is provided in Table S–1 (Screening, Baseline, and Treatment Period A) and Table S–2 (Treatment Period B, and Safety Follow-Up).

Study drug will be dispensed at the site during the Baseline visit when the visit is conducted in the clinic. For the remainder of the study, investigational product will be shipped directly to the subject. Study drug shipment, return, and accountability will be performed in accordance with the drug distribution plan.

The study start date is defined as the date the first subject is enrolled, which is the baseline visit date for the first subject.

The primary completion date is the last date that subject data was collected for the primary outcome measure.

The study completion date is defined as the last date that subject data was collected for the primary outcome measure, secondary outcome measure(s), and adverse events, which includes the safety follow-up telephone call visit.

Procedures for when a subject is lost to follow-up are provided in Section 4.5.

The Sponsor may discontinue the study for any reason.

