7.3 Time Period and Frequency for Event Assessment and Follow-up

Adverse events will be recorded from the time informed consent is obtained through the study safety follow-up period. If an AE is ongoing at the end of the study safety follow-up period, every reasonable attempt should be made to follow and appropriately treat the subject until the AE resolves or until the Investigator deems the AE to be chronic or stable.

In the event that a subject discontinues and has an ongoing AE at the time of discontinuation (Section 4.4.2) or is withdrawn from the study because of an AE, a blood sample should be collected and the subject should be followed and appropriately treated until the AE resolves or until the Investigator deems the AE to be chronic or stable.

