9.2 Statistical Hypotheses

This is an open-label and single arm study. All statistical analyses will be descriptive. No statistical hypothesis will be tested.

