9.3 Sample Size Determination

Approximately ten (10) to fifteen (15) subjects will be enrolled in this study, at least 1 subject who weighs ≥9 to <11 kg, and at least 4 subjects who are less than 4 years of age at Screening, including at least one subject who is 2 years of age. The sample size is not based on statistical considerations and is believed to be adequate to characterize the PK of trofinetide in this population.

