15.2 Adverse Events

Adverse events will be coded using MedDRA dictionary version 24.0.

An AE (classified by preferred term) will be considered a treatment-emergent AE (TEAE) if started after first dose administration and no later than last dose date + 30 days.

The event counts, the number, and percentage of subjects reporting TEAEs will be tabulated by system organ class (SOC) and PT; and by SOC, PT, and maximum severity. A subject is counted at most once per SOC and PT even if the subject has more than one TEAE. A subject is counted at most once per SOC and PT at the maximum severity for the summary by maximum severity. The display in these tables will be sorted alphabetically by SOC and then by descending subject frequency for the PTs within each SOC.

The event counts, the number and percentage of subjects with any TEAEs will also be tabulated by PT without SOCs. This table will be sorted by descending subject frequency.

Treatment-emergent SAEs, TEAEs leading to study drug withdrawn, and TEAEs related to study drug will be summarized by SOC and PT. The tables will be sorted alphabetically by SOC and then by descending subject frequency for the PTs within each SOC. In addition, the incidence of fatal treatment-emergent AEs (i.e., events that cause death) will be summarized separately by SOC and PT.

An AE listing by subject will display all events, including those which are not treatment-emergent, and will include the verbatim term in addition to the MedDRA SOC and PT. This listing will also include all relevant eCRF data associated with the event: date of onset, date

resolved, date of last dose, severity, frequency, outcome, relationship to study drug, and action taken with study drug. Separate listings will be presented for treatment-emergent SAEs, TEAEs leading to study drug withdrawn, fatal TEAEs (if any), and TEAEs related to COVID-19 infection.

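### An adverse event first seen in Screening that recurs on drug at the same severity can be left out of the TEAE tables for its preferred term, and the plan does not say whether it should be

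*Protocol*

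**What the plan says.** Five rules bear on this.

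- **Collection.** Protocol 7.3: "Adverse events will be recorded from the time informed consent is obtained through the study safety follow-up period". Protocol 3.1 gives the pre-dose window: "Screening period: up to 4 weeks".
- **Start date.** Protocol 7.2.3: "Date of the first episode of the AE or date of significant sustained worsening in severity".
- **Stop date.** Under the same section, a record ends when the event has ended for good or has worsened in severity. For diarrhea only, a decrease in severity is dated as well.
- **Frequency field.** Protocol 7.2.4 offers Single or Recurrent. Recurrent means "More than one discrete episode with the same severity".
- **Treatment emergence.** SAP 15.2 counts an event "if started after first dose administration and no later than last dose date + 30 days". It has no clause for an event that began before dosing and came back afterwards. The fallback in SAP 5.9, which resolves doubt towards treatment-emergent, applies only when a date is missing or incomplete.

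TEAEs are a primary safety endpoint (Protocol 2.1.1, SAP 15.1). Events that are not treatment-emergent appear only in the by-subject listing of SAP 15.2.

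**The concern.** Taken together, these rules let an on-drug event inherit a pre-dose start date. Suppose a girl vomits mildly once in Screening and then mildly several times on drug. Under a literal reading she has one Recurrent event that started before the first dose, and she is not a TEAE case for vomiting. The overall, related and withdrawal TEAE tables all draw on the same definition, so none of them shows her under that term.

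For such events the rule can remove girls from the count but never add them. Elsewhere the SAP resolves doubt the cautious way: unclear onset becomes treatment-emergent (5.9), missing severity becomes Severe (5.10) and missing causality becomes Related (5.11). Here it runs the other way. Protocol 1.5.1 names gastrointestinal effects as the most notable tolerability issue, and these are events that can also occur before dosing.

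The loss may not be recoverable at analysis. A merged record carries one start date. Protocol 6.4 specifies the caregiver diary for seizures and for dosing of study drug and concomitant medication, with no stated place for dates of gastrointestinal episodes.

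**Working it through.** The plan gives no figure to reproduce. Protocol 9.2 says "All statistical analyses will be descriptive. No statistical hypothesis will be tested", and Protocol 9.3 gives no sample-size formula. The check has two parts: apply the rules to a case, then gauge the size.

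**Rule check.** Mild vomiting on Day -14 recurs mildly on Day 10.

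- One merged record: start Day -14, so not a TEAE.
- Screening event closed and a new record opened: start Day 10, so a TEAE.
- Significant sustained worsening on Day 10: new start on Day 10, so a TEAE.

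The same clinical course is counted or not according to how the site keeps the record.

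**Size for vomiting.** Inputs are from Protocol Table 1-1 (Study 002): placebo 3/24, and 6/27 at 200 mg/kg BID. Treatment lasted 42 days (Protocol 1.3.2). The table also counts events after treatment, so the true window may be longer. I assume 42 to 72 days for the placebo rate; 72 is 42 plus an assumed 30 days and is not in the documents. Other assumptions are constant hazard, independence of pre-dose and on-drug events, equal severity, records always merged, and a full 28-day Screening.

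Chance q of a pre-dose vomiting event:

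- 42-day window: 1 − (1 − 3/24)^(28/42) = 8.5%
- 72-day window: 1 − (1 − 3/24)^(28/72) = 5.1%

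Chance p of vomiting on drug over the 84 days of Period A, taking 6/27 as a 42-day rate: 1 − (1 − 6/27)^(84/42) = 39.5%.

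A girl is lost with probability q × p, which is also the expected fall in incidence:

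- Low: 0.051 × 0.395 = 2.0 points
- High: 0.085 × 0.395 = 3.4 points

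Chance that at least one girl is lost:

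- N = 10, low: 1 − (1 − 0.020)^10 = 18%
- N = 15, high: 1 − (1 − 0.0336)^15 = 40%

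The expected number lost is 10 × 0.020 = 0.2 to 15 × 0.0336 = 0.5 girls. One girl is 1/15 = 6.7 to 1/10 = 10 points.

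The low end mixes windows. Applying 72 days to the treated rate too gives p = 1 − (1 − 6/27)^(84/72) = 25.4%. At N = 10 the chance of at least one loss is then 1 − (1 − 0.051 × 0.254)^10 = 12%, with an expected loss of 1.3 points.

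**Diarrhoea, for comparison.** Placebo 1/24 gives q = 1 − (1 − 1/24)^(28/42) = 2.8%. With 15/27 on drug, unscaled, the loss is 0.028 × 0.556 = 1.6 points, or 0.16 to 0.23 girls at N = 10 to 15.

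**Wider range.** With q from 5% to 30% and p from 20% to 80%, the loss runs from 0.05 × 0.20 = 1 point to 0.30 × 0.80 = 24 points. The documents give no basis for the upper end.

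**The case against.** The strongest reply is that merging across the first dose is an inference. No section requires it. Protocol 7.2.4 defines a descriptive field, introduced with a verb that the synopsis footnote defines as a recommendation. A single vomiting episode that resolved in Screening can fairly be judged to have ended for good, given the outcome recovered/resolved (7.2.7), and closed. The next episode is then a new event, in keeping with 7.4.1, which asks at each visit about events since the last one. This stands, and it limits the point: the plan permits the loss but does not impose it. It does not remove the point, because 7.2.3 and 7.2.4 can as readily be read the other way. With about 10 sites and 10 to 15 girls, a primary count could turn on local habit.

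Four further limits also stand.

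- Stable or intermittent chronic conditions that do not worsen are not adverse events (7.1.1), and events that worsen in severity get a new start date (7.2.3). Neither is affected.
- A reader might infer that the girl vanishes from the TEAE tables altogether. She is missing only for that preferred term. Any other TEAE keeps her in the overall row, and another gastrointestinal term keeps her in that system organ class. A discontinuation also appears in disposition (SAP 7).
- For diarrhea, a later decrease in severity is dated separately. If that opens a new record, it partly offsets the loss.
- A reader might take the chance that some girl has a pre-dose vomiting event, 1 − (1 − 0.051)^10 = 41% to 1 − (1 − 0.085)^15 = 74%, as the size. That is not the chance of a lost case, which also needs recurrence on drug. A figure for any gastrointestinal event fits no better: vomiting before dosing and diarrhoea after it are two events, and the second is counted.

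**Conclusion.** The gap is real and worth closing. A literal reading of Protocol 7.2.3 and 7.2.4 with SAP 15.2 leaves an on-drug recurrence out of a primary endpoint, and the alternative reading is neither required nor ruled out. The documents do not support the stronger statement that TEAE incidence is biased low. They support saying that it could be, for the preferred term concerned, and only downward.

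The effect is probably small: for vomiting in Period A, about an 18% to 40% chance of losing at least one girl and an expected loss of about 2 to 3 points. Those figures are upper-leaning, because they assume that every recurrence has the same severity and is merged, and the lower end drops to 12% if the longer window is used throughout. The point matters mainly because one girl moves incidence by 6.7 to 10 points in a study this size. SAP 1 shows that version 2.0 already revised the TEAE definition for Day 1 onset, so the pre-dose boundary was considered but recurrence was not covered.

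**What to change.** Make two changes.

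- **Protocol 7.2.3/7.2.4, or the eCRF completion guide.** State that, for an event first recorded before dosing, the first episode after the first dose opens a new record with its own start date.
- **SAP 15.2.** Define a TEAE as an event that started, recurred or worsened in severity after the first dose and no later than 30 days after the last.

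The recording rule is needed as well as the SAP clause, since a merged record does not hold the date of the recurrence. Leave out worsening in frequency: the Single/Recurrent field cannot support it.

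The cost is one sentence in each document and some site instruction. TEAE counts may rise slightly. Records already merged would need a query to the site for the date of the first post-dose episode.

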7.2.5 Action Taken with Study Drug

- **Dose not changed:** No change in study drug
- Dose decreased: Study drug dose decreased
- **Drug interrupted:** Study drug temporarily stopped

Final Version: 1.0

• Drug withdrawn: Study drug discontinued permanently

- Not applicable
- Unknown

7.2.6 Therapy

• None: No new treatment instituted

• **Medication:** New treatment initiated as a direct result of AE

• Other: Other action required

7.2.7 Outcome

• **Recovered/resolved:** Recovered or resolved

Recovered/resolved with sequelae: Recovered or resolved with sequelae

Not recovered/not resolved: Not recovered or not resolved

• Fatal: Death due to an AE

• **Unknown**: Unknown

7.2.8 Seriousness

- Not serious
- Serious (see Section 7.1.2)

7.2.9 Definition of Unexpectedness

An AE, the nature or severity of which is not consistent with the information provided in the Reference Safety Information section of the current trofinetide Investigator's Brochure.

7.3 Time Period and Frequency for Event Assessment and Follow-up

Adverse events will be recorded from the time informed consent is obtained through the study safety follow-up period. If an AE is ongoing at the end of the study safety follow-up period, every reasonable attempt should be made to follow and appropriately treat the subject until the AE resolves or until the Investigator deems the AE to be chronic or stable.

In the event that a subject discontinues and has an ongoing AE at the time of discontinuation (Section 4.4.2) or is withdrawn from the study because of an AE, a blood sample should be collected and the subject should be followed and appropriately treated until the AE resolves or until the Investigator deems the AE to be chronic or stable.

7.4 Reporting Procedures

7.4.1 Adverse Event Reporting

The Investigator must record all observed AEs and all reported AEs. At each visit, the Investigator should ask the subject and/or caregiver a nonspecific question (e.g., "Have you noticed anything different since your last visit?") to assess whether any AEs have been experienced since the last report or visit.

Note that any use of medication (and specifically any newly prescribed medication) during the course of a study may indicate the occurrence of an AE that may need to be recorded on both the AE and the concomitant medication page.

All AEs, serious and not serious, will be recorded on the AE eCRF page using appropriate medical terminology. Severity and relationship to study drug will be assessed by the Investigator.

When possible, clinical AEs should be described by diagnosis and not by symptoms (e.g., "cold" or "seasonal allergies" instead of "runny nose").

All AEs, whether or not related to the study drug, must be fully and completely documented on the AE eCRF and in the subject's notes.

7.4.2 Serious Adverse Event Reporting

The reporting of SAEs by the Sponsor or designee to the regulatory authorities is a regulatory requirement. Each regulatory authority has established a timetable for reporting SAEs based upon established criteria.

Serious AEs must be reported within 24 hours of discovery to the Sponsor or its designee; use the appropriate form for initial and/or follow-up reporting.

In the event an SAE or an AE leading to withdrawal is reported, a blood sample for determination of whole blood concentrations of trofinetide will be collected.

At a minimum, events identified by the Sponsor to require expedited reporting as serious, unexpected, and related to study drug must be brought to the attention of the responsible institutional review board/ethics committee (IRB/EC), as per applicable regulations. These will be provided by the Sponsor after their assessment. For European Union member states, the Sponsor or its designee will provide reports of suspected unexpected serious adverse reactions (SUSARs) directly to the ECs, as required by local legislation. In all other countries, it is the Investigator's responsibility to provide these expedited reports to the responsible IRB/EC. It is also the Investigator's responsibility to notify the responsible IRB/EC regarding any new and significant safety information.

Study: ACP-2566-009 Clinical Study Protocol Amendment 2

When an SAE occurs, Investigators will review all documentation related to the event and will complete the paper SAE form with all required information (for initial and/or follow-up information) and fax or email (within 24 hours of discovery) to the contact information provided on the SAE form.

Subjects will be followed through the safety follow-up period (i.e., 30[+4] days after last dose of study drug) for any SAEs and/or other reportable information until such events have resolved or the Investigator deems them to be chronic or stable.

In the event of any SAE (other than death), the study subject's caregiver will be instructed to contact the Investigator (or designee) using the telephone number provided in the ICF. All subjects experiencing an SAE will be seen by the Investigator or designee as soon as is feasible following the report of the SAE.

Serious AEs occurring after the study follow-up period (i.e., 30[+4] days after last dose of study drug) should be reported if in the judgment of the Investigator there is "a reasonable possibility" that the event may have been caused by the product.

SAEs should also be reported to the IRB/EC according to local regulations.

7.4.3 Reporting of Overdose

An overdose is a deliberate or inadvertent administration of a treatment at a dose higher than the maximum recommended dose per protocol. It must be reported to the Sponsor or designee on the Overdose form within 24 hours of discovery. In addition, all events of overdose are to be captured as protocol deviations.

8 CLINICAL MONITORING

Routine monitoring of study sites is described in Section 11.2.

Clinical site monitoring is conducted to ensure that the rights and well-being of human subjects are protected, that the reported study data are accurate, complete, and verifiable, and that the conduct of the study is in compliance with the currently approved protocol and amendment(s) as applicable, with GCP, and with applicable regulatory requirements. Details of the study site monitoring process are described in a separate clinical monitoring plan document.

9 STATISTICAL METHODS AND DATA ANALYSIS

9.1 Statistical and Analytical Plans

Statistical methods will be documented in detail in a statistical analysis plan (SAP) to be approved by the Sponsor prior to database lock. Deviations from the approved SAP will be described and justified in the final clinical study report.

Final Version: 1.0

9.2 Statistical Hypotheses

This is an open-label and single arm study. All statistical analyses will be descriptive. No statistical hypothesis will be tested.

9.3 Sample Size Determination

Approximately ten (10) to fifteen (15) subjects will be enrolled in this study, at least 1 subject who weighs ≥9 to <11 kg, and at least 4 subjects who are less than 4 years of age at Screening, including at least one subject who is 2 years of age. The sample size is not based on statistical considerations and is believed to be adequate to characterize the PK of trofinetide in this population.

9.4 Subject Populations for Analysis

The following populations will be defined and used in the analysis:

The **Safety Analysis Set** will consist of all enrolled subjects who received at least one dose of study medication. This analysis set will be used for all safety as well as any descriptive efficacy analyses.

The **PK Analysis Set** will consist of all subjects who receive at least 1 dose of study drug and have sufficient blood concentration data to calculate at least one PK parameter.

9.5 Statistical Analyses

9.5.1 General Approach

Continuous measurement results will be reported using the number of subjects with data values, mean, standard error of the mean, median, standard deviation, minimum, and maximum. For each categorical outcome, the number and percentage of subjects in each category will be reported.

9.5.2 Safety Analyses

Safety results will be summarized using descriptive statistics. Adverse events will be coded into standard terminology using the Medical Dictionary for Regulatory Activities (MedDRA). Treatment-emergent adverse events (TEAEs), TEAEs leading to discontinuation, TEAEs considered related to study drug, TEAEs by maximum severity, and serious adverse events (SAEs) reported after study medication start, will all be summarized.

Descriptive statistics for ECG, vital signs and weight, and clinical laboratory parameters, including changes from Baseline, will be tabulated by timepoint. Additionally, categorical analyses will be conducted on the incidence of subjects with prolonged QTc (QT interval of ECG corrected for heart rate) intervals and changes in QTc intervals in accordance with International Council for Harmonisation (ICH) guidelines.

Additional safety analysis details will be specified in the SAP.

